8.7 Vital Signs and Physical Evaluations

Vital signs measurements include temperature, pulse, and systolic and diastolic blood pressure. The assessment of vital signs is planned at week 0, 4, 8, 16, 24, 32, 40, 48, 56, 64 and 72. The physical exam is only required at the screening visit and may be performed at subsequent visits if needed based on interim history. These optional physical exam evaluations are not captured in the data system.

Vital signs are tabulated by visit, age stratum, and treatment group. Vital signs will be summarized over time graphically using box plots for subjects in the Safety population (**Table 14.3.5, Appendix I, Figure 14.4.1-14.4.x, Appendix II, Listing 16.2.9, Appendix III**).

9 IMMUNOGENICITY EVALUATION

Specimens to evaluate immunogenicity will be taken at baseline and at specified time points. The primary immunogenicity timepoint is 4 weeks after the second injection. Measurements of CHIKV-specific humoral immune responses will be assessed by neutralization antibody (NAb) assays. A listing of individual titer levels and the corresponding planned and actual collection dates are presented in **Appendix III, Listing 16.2.6**.

At some sites, positive baseline Week 0 neutralization antibody assay results were reported. ELISA response data, captured as part of the screening eligibility process, have been received by the Sponsor from the laboratory. When raw ELISA data is received, baseline ELISA responses will be assessed in relation to neutralization antibody data and results will be reported. For further information, a separate analysis plan will be created to elaborate on specific analyses to be performed.

The principle immunogenicity endpoint is measured at Week 8 by neutralization assay.

Descriptive analyses will be presented by study day, age group, and treatment group, aggregated over all study sites and by site. If none or a very small number of placebo group subjects have a neutralization response, their results will only be reported for the positive response rate summaries and omitted from other analyses. This approach is taken to achieve brevity and easier understanding of results when the control group has no meaningful responses.

Summaries include:

- GMT and their confidence intervals (**Table 14.2.1, Appendix I**)
- Geometric mean ratio (GMR) of results obtained at baseline (Week 0) to results obtained at Week 8 and its 95% CI. (**Table 14.2.1, Appendix I**)
- Positive response rates, as defined by an assay-specific post dose response, and their exact 95% CI (**Table 14.2.1, Appendix I**)
- Reverse cumulative distribution of the neutralization assay results (**Figure 14.2.1, Appendix II**)
- Boxplots of titer values (**Figure 14.2.2, Appendix II**).

These summaries will be repeated for all exploratory research tests used to measure exploratory immunogenicity endpoints at the timepoints for which there are data.

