Month and Year	[Site 1] CHIKV (N=X)	[Site 1] Placebo (N=X)	[Site 2] CHIKV (N=X)	[Site 2] Placebo (N=X)	[Site 3] CHIKV (N=X)	[Site 3] Placebo (N=X)	[Site 4] CHIKV (N=X)	[Site 4] Placebo (N=X)	[Site 5] CHIKV (N=X)	[Site 5] Placebo (N=X)	[Site 6] CHIKV (N=X)	[Site 6] Placebo (N=X)	All Sites CHIKV (N=X)	All Sites Placebo (N=X)	All Sites All Subjects (N=X)
November 2015	x	x	x	x	x	x	x	x	x	x	X	x	x	x	x
December 2015															
...															

Section 14.2 Immunogenicity Data

TABLE 14.2.1:
Geometric Mean Titer (GMT), Geometric Mean Ratio, and Positive Response Rates of the [specific strain/assay] Results with 95% Confidence Intervals at Baseline and Week 8 by Site and Treatment Group <<Age Stratum>>

Treatment Group	Baseline		Week 8		Comparison of GMT at Week 8 (p-value)	Geometric Mean Ratio (95% CI)	P-value comparison of GMR	Positive Response Rates (%) at Week 8 (95% CI)^	P-value comparison of Positive Response Rates*
	N	GMT (95% CI)	N	GMT (95% CI)					
Overall									
CHIKV VLP 20 mcg	x	xx.x (xx.x, xx.x)	x	xx.x (xx.x, xx.x)	x.xxx	x.xx (x.xx, x.xx)	x.xxx	xx.x (xx.x, xx.x)	x.xxx
PBS									
Site 1 [repeat for all sites]									
CHIKV VLP 20 mcg									
PBS									

GMT = Geometric Mean Titer, CI = Confidence Interval, GMR = Geometric Mean Ratio
 ^Positive immune response defined as [positivity criteria here]
 *p-value from Fisher's exact test

Section 14.3 Safety Data

**TABLE 14.3.1.1:
 Number and Percentage of Subjects Experiencing Solicited Events with 95% Confidence Intervals by Symptom,
 Dose, Treatment Group, and Site <<Age Stratum>>**

[Implementation note: Repeat rows for each site like the example at the end of the table for Site 1]

Symptom	Post Dose 1 CHIKV (N=X)			Post Dose 1 Placebo (N=X)			Post Dose 2 CHIKV (N=X)			Post Dose 2 Placebo (N=X)			Post Either Dose CHIKV (N=X)			Post Either Dose Placebo (N=X)		
	n	%	95% CI	n	%	95% CI	n	%	95% CI	n	%	95% CI	n	%	95% CI	n	%	95% CI
Overall																		
Any Symptom	x	x.x	x.x, x.x	x	x.x	x.x, x.x	x	x.x	x.x, x.x	x	x.x	x.x, x.x	x	x.x	x.x, x.x	x	x.x	x.x, x.x
Any Systemic Symptom																		
Nausea																		
Chills																		
Headache																		
Malaise [Unusually Tired/Feeling Unwell]																		
Myalgia [Muscle/Body Aches]																		

TABLE 14.3.1.1: Number and Percentage of Subjects Experiencing Solicited Symptoms with 95% Confidence Intervals by Symptom, Dose and Treatment Group (continued)

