Appendix II: Figure Mock- Ups

for

VRC 704

Study Title:

**Phase 2 Randomized, Placebo-Controlled Trial to Evaluate the Safety and Immunogenicity of a
Chikungunya Virus-Like Particle Vaccine,
VRC-CHKVLP059-00-VP, in Healthy Adults**

Version 1.0

Prepared and distributed by:
The Emmes Corporation
Rockville, Maryland

THIS COMMUNICATION IS PRIVILEGED AND CONFIDENTIAL

Table of Contents

FIGURE 14.1.1: CONSORT Flow Diagram By Age Stratum.....	2
FIGURE 14.2.1: Reverse Cumulative Distribution of the Assay by Study Day, Site, and Treatment Group.....	3
FIGURE 14.2.2: Boxplots with Overlaid Scatter Plots Summarizing the Assay by Study Day, Site, and Treatment Group.....	4
FIGURE 14.3.1.1: Maximum Severity per Subject by Days Post Treatment	5
FIGURE 14.3.1.2: Number and Severity of Non-Serious Adverse Events by MedDRA® System Organ Class	6
FIGURE 14.3.1.3: Non-Serious Adverse Events by Severity	7
FIGURE 14.3.1.4: Number and Relationship of Non-Serious Adverse Events by MedDRA® System Organ Class	8
FIGURE 14.3.1.5: Non-Serious Adverse Events by Relationship to Treatment.....	10
FIGURE 14.3.4.1: Laboratory Results by Scheduled Visits: Mean Changes from Baseline by Laboratory Parameter and Treatment Group.....	11
FIGURE 14.4.1-14.4.x: Boxplot of Vital Signs by Scheduled Visits	12
FIGURE 14.5.1-14.5.x: Boxplot of Laboratory Results by Scheduled Visits.....	13
FIGURE 15.1.1: Kaplan-Meier Curves for Time to Occurrence of Clinical CHIKV Infection Post Dose One	14
FIGURE 15.1.2: Kaplan-Meier Curves for Time to Occurrence of Clinical CHIKV Infection Post Dose Two	14
FIGURE 15.1.3: Kaplan-Meier Curves for Time to Occurrence of PCR Confirmed CHIKV Infection Post Dose One	14
FIGURE 15.1.4: Kaplan-Meier Curves for Time to Occurrence of PCR Confirmed CHIKV Infection Post Dose Two.....	14

**FIGURE 14.1.1:
 CONSORT Flow Diagram By Age Stratum**

[Implementation Note: In the SAP, include a blank diagram with the possible reasons why subjects may be excluded from analyses. The reasons for exclusion should be in line with the SAP text.]

[figure not shown]

FIGURE 14.2.1:
Reverse Cumulative Distribution of the [specific assay] by Study Day, Site, and Treatment Group <<Age Stratum>>

Note: These are illustrative curves. The actual curves compare CHIKV vaccine and placebo. For neutralization (the primary immunogenicity endpoint), the time periods to be used are Days 0, 28 and 56.

[figure not shown]

FIGURE 14.2.2:

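### An undefined rule in SAP Section 9 can remove placebo titre summaries that the shells plan, and the response rate that remains ignores baseline antibody

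*Combined protocol and SAP*

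**What the plan says.** SAP Section 9 lists five neutralization summaries: GMT, GMR between Week 0 and Week 8, positive response rate, reverse cumulative distribution and boxplots. They are to be given by treatment group, pooled and by site. It then makes an exception, with this trigger: "If none or a very small number of placebo group subjects have a neutralization response". The size of a very small number is not stated, nor is the visit, the population (ITT, PP or mITT), or whether the trigger is judged overall, by age stratum or by site. When the trigger is met, the consequence for the placebo arm is that "their results will only be reported for the positive response rate summaries and omitted from other analyses". The reason given is presentational: "This approach is taken to achieve brevity and easier understanding of results when the control group has no meaningful responses".

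The shells assume both arms. Table 14.2.1 in SAP Appendix I has a PBS row, overall and for each site, and three between-arm p-values: Week 8 GMT, "P-value comparison of GMR" and "P-value comparison of Positive Response Rates". The note to Figure 14.2.1 in Appendix II says "The actual curves compare CHIKV vaccine and placebo". None of these shells mentions an omission. Protocol Section 6.4 likewise plans descriptive statistics by vaccine group and methods for comparing geometric means.

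Two other statements matter. SAP Section 3.3 sets values below the limit of detection to 15 and defines a positive response as a titre of 30 or more, with no condition on baseline. And Section 9 records that "At some sites, positive baseline Week 0 neutralization antibody assay results were reported".

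**The concern.** Whether the titres of the randomised control are summarised depends on the observed results, through a threshold that someone must choose after seeing them. That is avoidable in a plan written in advance, and it contradicts the plan's own shells.

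The stake is interpretive. The participants live in endemic areas, so the placebo arm is the control for natural exposure and for assay drift between Day 0 and Week 8. PCR testing is prompted by reported signs and symptoms (SAP Section 4.6.3), so a rise in placebo titre is the natural check on exposure without symptoms. What the rule keeps is a Week 8 proportion at or above 30. That cannot show whether a positive placebo subject was already positive at Week 0. The placebo baseline GMT and GMR can, and the rule would remove them. Since some sites already have positive Week 0 titres, the question is a live one.

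**Working it through.** **Inputs.** 200 per arm less 10% loss gives 180 (SAP Section 5). Vaccine log mean at peak is 7.41, with SD rounded to 0.70 (SAP 5.2). Values below detection are set to 15 and a response is a titre of 30 or more (SAP 3.3). The plan gives no omission threshold and no expected placebo positive rate, so both are varied below as assumptions.

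**1. The plan's own figure.** SAP Table 4, SD 0.70: exp(7.41 ± t × 0.70/√180), with t on 179 degrees of freedom, gives 1490.8 to 1831.6, against the stated 1490.7 to 1831.7. It reproduces within rounding, so the scale is natural log and the vaccine GMT is exp(7.41), about 1652.

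**2. How far the missing cutoff matters.** If X is the number of placebo responders, binomial with n = 180 and rate p, the rule fires with probability P(X ≤ c) for cutoff c:

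| Assumed true placebo rate | c = 0 | c = 2 | c = 5 | c = 9 |
|---|---|---|---|---|
| 1% | 16% | 73% | 99% | about 100% |
| 2% | 3% | 30% | 85% | 99.6% |
| 5% | about 0% | 0.5% | 11% | 59% |

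At 2%, the choice of cutoff alone moves omission from improbable to almost certain.

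**3. Omission is not a numerical need.** With k responders at titre T and the rest at 15, placebo GMT = 15 × (T/15)^(k/180). Take T = 1000 as an assumption. The vaccine/placebo ratio is exp(7.41)/GMT, with 95% limits from ±1.96 × √(0.70²/180 + s²/180) on the log scale, where s is the placebo log SD.

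| Placebo responders | Placebo GMT | Ratio (95% CI) |
|---|---|---|
| 0 | 15.0 | 110 (99.5 to 122) |
| 5 | 16.9 | 98 (85 to 113) |
| 9 | 18.5 | 89 (75 to 106) |
| 18 | 22.8 | 72 (59 to 89) |

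Every line can be computed, including the one with no responders. The ratio stays very large throughout.

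**4. What survives.** The placebo response rate keeps its exact interval: 5 of 180 is 2.8% (0.9% to 6.4%). The Fisher comparison also stays: 180/180 against 5/180 gives p < 0.001.

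**5. What the surviving rate cannot show.** Take five placebo responders at titre 1000 at Week 8, all others at 15 at both visits, and GMR as Week 8 over Week 0.
- All five already at 1000 at Week 0: Week 8 rate 2.8%, placebo GMR 16.9/16.9 = 1.00.
- All five at 15 at Week 0: Week 8 rate 2.8%, placebo GMR 16.9/15 = 1.12.

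The rate is the same in both; only the GMR differs. Pooled, the difference is small. Within a site it need not be. If six sites shared 180 placebo subjects equally (30 each, an assumption; the shells show six sites) and all five were at one site, that site's Week 8 GMT would be 15 × (1000/15)^(5/30) = 30.2. Its GMR would be 1.0 in the first case and 30.2/15 = 2.0 in the second. A trigger judged on the pooled count of five could suppress that contrast.

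**The case against.** The rule is written in advance and its reason is stated. It is also largely self-limiting. Exposure, upward drift or persisting antibody that takes placebo subjects to 30 or more makes them responders, which raises the rate that is always reported and makes omission less likely. When almost every placebo value is 15, the placebo GMT is about 15 and the GMR about 1, so little is lost. The secondary objective, unlike the primary, does not mention placebo. SAP 6.8 says that no specific hypothesis is tested, and SAP 5.2 gives the placebo comparison little weight for sample size. Eligibility required a negative antibody screen. Section 9 also promises a separate plan relating baseline ELISA to neutralization data.

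Most of this stands, and it rules out three stronger readings that a reader might infer:
- That the control arm goes unreported. It does not: its response rate with exact interval remains, and Listing 16.2.6 gives individual titres with treatment group.
- That the planned between-arm comparisons become impossible. The rule is conditional, the Fisher comparison survives, and the GMT and GMR comparisons would be left out rather than be incalculable.
- That the vaccine rise cannot be attributed at sites with baseline antibody. Many positive placebo subjects should stop the rule firing on an ordinary reading; if there are few, the low Week 8 rate is itself informative. Attribution is harder there, not lost.

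The objection does not answer two things. The cutoff and its level are still undefined, and the shells still contradict the text. And where a few placebo subjects were positive at baseline, perhaps at one site, the retained rate cannot say whether their titres changed. A listing lets a reader work that out but is not a summary.

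**Conclusion.** The point holds as an avoidable, data-dependent reporting rule that conflicts with Table 14.2.1 and Figure 14.2.1. If it fires, two of three between-arm p-values and the placebo curves and boxplots are not produced.

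The effect on the main conclusion is likely to be small: a vaccine GMT near 1650 against 15 to 23 for placebo with up to 18 responders in the illustration. That rests on the Phase 1 peak-visit mean and SD holding at Week 8, on non-responders sitting at 15, and on the assumed responder titre of 1000. The practical loss is confined to interpreting the rise at sites with positive Week 0 titres. The documents do not say how many subjects or which sites these are, so its size cannot be fixed.

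**What to change.** Delete the conditional sentence in SAP Section 9, with the sentence justifying it. State instead that GMT, GMR, positive response rate, reverse cumulative curves and boxplots are presented for both arms in all cases, overall and by site. The existing shells already have this layout and need no redesign. The cost is a few table rows and plot lines; the only loss is brevity.

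If the sponsor wants to keep an omission rule, the second-best course is to fix a numeric cutoff before titres are linked to treatment. It should name the visit, population, baseline status and the level at which it is judged, and the shells should be footnoted to match. That removes the discretion, but it would still leave placebo baseline titres and fold-rise unsummarised whenever the rule fires.

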10 ANALYSES OF CHIKUNGUNYA INFECTION INCIDENCE AND TIME TO EVENT

Analyses of CHIKV infections are exploratory. A few definitions of incident cases exist and therefore efficacy will be considered in:

- cases for which CHIKV is confirmed by a positive PCR
- cases with symptoms consistent with CHIKV but not necessarily confirmed by a positive PCR

Efficacy will include all cases using 2 exploratory alternatives for case inclusion:

1. all infections post dose 1 (Day 0),
2. all infections post dose 2.

Subjects not receiving dose 2 will be included in definition 1.

The analysis of efficacy is divided into two parts which are described below, using the intent-to-treat cohort.

Clinical cases as well as PCR confirmed cases are listed in **Listing 16.3.1, Appendix III**. Individual time to event data post dose one and post dose two are listed in **Listing 16.3.2 -16.3.3, Appendix III**.

10.1 Description of Observed Events:

- Incidence and number of clinical cases of CHIKV
 - Inclusion 1: All cases post dose 1 (Day 0)
 - Inclusion 2: All cases post dose 2. Subjects not receiving dose 2 will be considered for inclusion 1.
- Incidence and number of PCR confirmed cases of CHIKV
 - Inclusion 1: All cases post dose 1 (Day 0)
 - Inclusion 2: All cases post dose 2. Subjects not receiving dose 2 will be considered for inclusion 1.

For each scenario, incidence rates and number of cases will be described by treatment group by age stratum and aggregating and by combining age strata. Results are presented in **Tables 15.1.1-15.1.4 in Appendix I**.

10.2 Analysis of Vaccine Efficacy:

- Time to occurrence of clinical CHIKV infection
 - Inclusion 1: All cases post dose 1 (Day 0)
 - Inclusion 2: All cases post dose 2. Subjects not receiving dose 2 will be considered for inclusion 1.
- Time to occurrence of PCR confirmed CHIKV infection
 - Inclusion 1: All cases post dose 1 (Day 0)
 - Inclusion 2: All cases post dose 2. Subjects not receiving dose 2 will be considered for inclusion 1.

Time to event will be based on the date of onset of the clinical symptom (for clinical cases) or on blood sample with the first positive laboratory test indicating CHIKV infection (for PCR confirmed cases).

Time to occurrence post dose one and post dose two will be calculated for clinical CHIKV infections as well as PCR confirmed CHIKV infections as follows:

Post first injection:

- For subjects with infection: First date of diagnosis of clinical CHIKV infection minus date of first injection + 1. These subjects will not be censored.
- For subjects with no infection: Date of study completion or date of early termination minus date of first injection + 1. These subjects will be censored at their date of study completion or date of early termination.

Post second injection:

- For subjects with infection: First date of diagnosis of clinical CHIKV infection minus date of second injection + 1. These subjects will not be censored.
- For subjects with no infection: Date of study completion or date of early termination minus date of second injection + 1. These subjects will be censored at their date of study completion or date of early termination.
- Subjects that do not receive the second dose are excluded.
- Subjects that develop CHIKV before second dose are excluded.

The principal exploratory analysis consists of a comparison between the vaccine and placebo groups of the time to occurrence of infection after first dose and after second dose. The magnitude of vaccine effect will be estimated in terms of vaccine efficacy (95% CI) obtained from Cox proportional hazard model. Statistical testing will be performed using Log-rank test. (**Tables 15.2.1-15.2.4, Appendix I**)

The secondary exploratory analysis consists of an adjusted survival for age and site using a Log-rank test. In addition to univariate adjustments, multivariate adjustment will be performed in a single model using Cox regression for time to infection after first dose and after second dose. Estimates of vaccine efficacy adjusting for baseline characteristics will be displayed in **Tables 15.3.1-15.3.4, Appendix I**. Kaplan-Meier survival curves will be plotted by group, as presented in **Figures 15.1.1-15.1.4 Appendix III**.

10.3 Sample SAS Code for Analysis:

Notations

Timevar = the variable that gives the time to occurrence

Censor_var = the variable defining whether timevar is censored

Trtmnt_group = treatment group where 0 = Placebo and 1=VRC-CHIKVLP059-00-VP;

Cox Proportional Hazard

SAS Code for Cox Regression to obtain Vaccine Efficacy and 95% CI for Vaccine Efficacy:

```
Proc phreg;
```

```
Model timevar*censor_var(0)=trtmnt_group (and any covariates)/rl;
```

```
Ods output parameterestimates=ests(keep=HazardRatio HRUpperCL HRLowerCL);
```

```
Run;
```

```
Ods output RiskDiffCol1=rde1;
```

```
Run;
```

Calculate the following from the hazard ratios/estimates obtained from SAS

Vaccine Efficacy = 1 – Hazardratio;

Lower 95% CI= 1 – HRUpperCL which is the same as $1 - \exp(\text{estimate} + 1.96 * \text{stderr})$

Upper 95% CI= 1 – HRLowerCL which is the same as $1 - \exp(\text{estimate} - 1.96 * \text{stderr})$

Log-Rank Test

SAS Code for Log-Rank Test to obtain p-value:

```
Proc lifetest;
```

```
time timevar*censor_var(0);
```

```
strata trtmnt_group;
```

```
id pid;
```

```
Ods output homtests = tests(where=(test="Log-Rank") keep=test probchisq);
```

```
Run;
```

Obtain p-value from SAS: p-value=probchisq;

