6.4.4. Analysis of Chikungunya Incidence

Incidence rates for confirmed CHIKV cases will be described by vaccine group by age stratum and aggregating and by combining age strata. Results will be treated both as dichotomous (infection, no infection) and as a time to event (infection) variables. Time to event will be based on the date of blood sample with the first positive laboratory test indicating CHIKV infection. For each approach, infection rates in each treatment arm and vaccine efficacy along with their corresponding 95% CI will be computed. Efficacy for dichotomized data will be computed by a simple conversion of the relative risk to efficacy. Time to infection data, accounting for censoring, will be described using Kaplan Meir curves and efficacy computed using a Cox proportional hazards model.

Analyses of CHIKV infections are exploratory. A number of definitions of incident cases and therefore efficacy will be considered. Given the exploratory nature of these analyses, no order of primacy will be defined.

Efficacy will include all cases using 2 exploratory alternatives for case inclusion:

1. all infections post vaccination 1 (Day 0),
2. all infections post vaccination 2,

Subjects not receiving vaccination 2 will be included in definition 1. The SAP will provide any necessary additional specificity and/or cohort definitions such as discussed at the beginning of section 6.4.

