Subject Disposition	Site 1 CHIKV (N=X)		Site 1 Placebo (N=X)		Site 2 CHIKV (N=X)		Site 2 Placebo (N=X)		Site 3 CHIKV (N=X)		Site 3 Placebo (N=X)		Site 4 CHIKV (N=X)		Site 4 Placebo (N=X)		Site 5 CHIKV (N=X)		Site 5 Placebo (N=X)		Site 6 CHIKV (N=X)		Site 6 Placebo (N=X)		All Sites CHIKV (N=X)		All Sites Placebo (N=X)		All Sites All Subjects (N=X)	
	n	%	n	%	n	%	n	%	n	%	n	%	n	%	n	%	n	%	n	%	n	%	n	%	n	%	n	%	n	%
Enrolled	x	x.x	x	x.x	x	x.x	x	x.x	x	x.x																				
ChikV infection confirmed by PCR																														
ChikV infection prior to second injection																														
Received second injection and not ChikV infected																														
ChikV infected post second injection																														
Completed follow-up in PP Cohort without infection																														
Lost to follow-up and not known to be infected																														
Completed ITT Cohort without ChikV infection																														
Clinical ChikV infection (confirmed or not by PCR)																														
ChikV infection prior to second injection																														
Received second injection and not ChikV infected																														
ChikV infected post second injection																														

Subject Disposition	Site 1 CHIKV (N=X)		Site 1 Placebo (N=X)		Site 2 CHIKV (N=X)		Site 2 Placebo (N=X)		Site 3 CHIKV (N=X)		Site 3 Placebo (N=X)		Site 4 CHIKV (N=X)		Site 4 Placebo (N=X)		Site 5 CHIKV (N=X)		Site 5 Placebo (N=X)		Site 6 CHIKV (N=X)		Site 6 Placebo (N=X)		All Sites CHIKV (N=X)		All Sites Placebo (N=X)		All Sites All Subjects (N=X)				
	n	%	n	%	n	%	n	%	n	%	n	%	n	%	n	%	n	%	n	%	n	%	n	%	n	%	n	%	n	%			
Completed follow-up in PP Cohort without infection																																	
Lost to follow-up and not known to be infected																																	
Completed ITT Cohort without ChikV infection																																	

TABLE 14.1.5:
Distribution of Subject-Specific Protocol Deviations by Category and Treatment Group

Category	CHIKV (N=X)		Placebo (N=X)		All Subjects (N=X)	
	# of Subj.	# of Dev.	# of Subj.	# of Dev.	# of Subj.	# of Dev.
Eligibility/enrollment						
Product administration schedule						
Follow-up visit schedule						
Protocol procedure/assessment						
Product administration						
Blinding policy/procedure						

TABLE 14.1.6.1:
Distribution of Sex, Ethnicity, Race, and Language by Site

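### SAP 10.2 says PCR-confirmed infections are dated by the first positive sample, but its only event-time formulas use the first clinical CHIKV diagnosis, which need not be PCR-confirmed

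*Combined protocol and SAP*

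**What the plan says.** SAP 10.2 first gives a dating rule for each endpoint. For clinical cases: "Time to event will be based on the date of onset of the clinical symptom (for clinical cases"). For PCR-confirmed cases: "or on blood sample with the first positive laboratory test indicating CHIKV infection (for PCR confirmed cases"). Protocol 6.4.4 has the same rule for laboratory-confirmed cases: "Time to event will be based on the date of blood sample with the first positive laboratory test indicating CHIKV infection". The symptom-onset rule appears only in the SAP.

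The SAP then says that time to occurrence "will be calculated for clinical CHIKV infections as well as PCR confirmed CHIKV infections as follows". Only one formula per injection follows. After the first injection it is "First date of diagnosis of clinical CHIKV infection minus date of first injection + 1"; after the second it is "First date of diagnosis of clinical CHIKV infection minus date of second injection + 1". There is no PCR formula.

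A clinical case does not require confirmation. SAP section 10 describes "cases with symptoms consistent with CHIKV but not necessarily confirmed by a positive PCR", and Table 14.1.4 has the row "Clinical ChikV infection (confirmed or not by PCR").

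For the post-dose-2 analysis, SAP 10.2 also removes subjects who developed CHIKV before the second dose. It does not say whether that means clinical or PCR-confirmed CHIKV.

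**The concern.** The formula is what a programmer codes, and it conflicts with the rule stated just above it. For the PCR endpoint it substitutes a clinical diagnosis date, and it takes the first such date. If a subject has a CHIKV-like illness that is PCR-negative or untested, and later a PCR-confirmed infection, the earlier illness would date the PCR event. The formula also misses the SAP's own clinical rule, because a diagnosis date is not a symptom-onset date.

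SAP 4.6.3 names PCR-confirmed illness as the primary variable for the incidence analysis. The derived time feeds the Cox and log-rank results (Tables 15.2.3-15.2.4 and 15.3.3-15.3.4), the Kaplan-Meier curves (Figures 15.1.3-15.1.4) and Listing 16.3.3. It may also affect who is counted after dose 2.

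**Working it through.** The plan states no figure to reproduce here. The check compares the texts and then works through illustrations.

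**Which date is the outlier?**

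| Place | Clinical endpoint | PCR endpoint |
|---|---|---|
| SAP 10.2, stated rule | symptom onset | first positive sample |
| Protocol 6.4.4 | not given | first positive sample |
| Listings 16.3.2 and 16.3.3, date column | symptom date | PCR confirmation date |
| SAP 10.2, formulas | first clinical diagnosis | first clinical diagnosis |

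The formulas stand alone against the other three sources.

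**Size of the date shift.** Time = event date − injection date + 1. Assume dose 1 on day 0, dose 2 on day 28 (the planned interval) and the first PCR-positive sample on day 300. The stated rule gives 300 − 0 + 1 = 301 days after dose 1 and 300 − 28 + 1 = 273 days after dose 2. The formula gives:

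| First clinical diagnosis | After dose 1 | After dose 2 | Shift |
|---|---|---|---|
| day 300, same illness | 301 | 273 | 0 |
| day 298, same illness | 299 | 271 | 2 days |
| day 60, separate PCR-negative illness | 61 | 33 | 240 days |
| day 14, separate PCR-negative illness | 15 | −13 | 286 days; time after dose 2 is not positive |

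**Effect of re-dating on VE.** The documents give no case counts. Assume 200 per arm with 8 placebo and 2 vaccine PCR cases. The Cox model uses only the order of events and the composition of the risk sets. Moving one event earlier therefore changes little when each arm has about 200 subjects at risk. In 200 simulated datasets, moving one case to day 15 changed Cox VE by at most 0.3 percentage points (mean 0.07). A separate run of 300 datasets with an assumed 10% random dropout gave at most 0.4 points (mean 0.08). The Kaplan-Meier curve of the affected arm moves by about 1/200 = 0.5 points between the wrong and the right date.

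**Effect of losing a case on VE.** Use the same assumed counts with equal arms, and take VE as 1 minus the ratio of cases:
- All cases kept: 1 − 2/8 = 75%.
- One placebo case lost: 1 − 2/7 = 71%.
- One vaccine case lost: 1 − 1/8 = 87.5%.

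A case is lost only through the day-14 type of history. Either the non-positive time makes the record unusable, or the pre-dose-2 exclusion is read to include unconfirmed illness.

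**The case against.** The best reply is that the intended date is clear. The sentence above the formulas, protocol 6.4.4 and the endpoint-specific date columns in the listings all agree, and a programmer filling Listing 16.3.3 would notice the conflict. That makes a drafting slip likely. It does not remove the problem, because the formula is the operative instruction and nothing in the SAP says which text prevails.

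A reader might infer that a shift of months in one event date would visibly distort VE. The planned estimator does not support that, as the simulations show. The movements to 71% and 87.5% come from deleting a case. They depend on the pre-dose-2 exclusion, which would be ambiguous even with a correct PCR formula.

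The deletion scenario is also narrow. One subject must have a separate unconfirmed illness between the two doses (28 days, up to 42 with the window), still receive dose 2, and later have a PCR-confirmed infection. The plan calls for sampling when symptoms are reported, so within one illness the two dates should be close. An error approaching the 72-week follow-up is a theoretical ceiling, and the documents give no frequency for two illnesses in one subject.

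Precision matters too. With 8 and 2 cases, the standard error of the log hazard ratio is about √(1/8 + 1/2) = 0.79. The 95% interval for VE is then 1 − exp(−1.386 ± 1.96 × 0.79), roughly −18% to 95%. A 4-point change is small beside that.

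**Conclusion.** Wrong as written, of minor severity. The formulas contradict the SAP's stated dating rule for both endpoints, and for the PCR endpoint they also contradict the protocol. Literal use would usually move a PCR event time by days, and by months only for a subject with two separate illnesses. Re-dating alone affects Kaplan-Meier curves and listed times; its effect on Cox VE is a fraction of a point. A change of about −4 or +12.5 points in VE requires the loss of a true post-dose-2 PCR case. All VE figures rest on the assumed 8 and 2 cases and 200 per arm. The documents do not support any wider inference: the infection analyses are exploratory, protocol 6.4.4 sets no order of primacy among the case definitions, and the Week 8 neutralization summaries do not use this derived event time.

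**What to change.** Replace the shared formula in SAP 10.2 with two, each applied to both injections:
- Clinical endpoint: symptom-onset date − injection date + 1.
- PCR endpoint: collection date of the first PCR-positive sample − injection date + 1.

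State that the same endpoint-specific date decides whether a subject had CHIKV before dose 2, so that an unconfirmed illness does not remove a subject from the PCR analysis. Listings 16.3.2 and 16.3.3 already have endpoint-specific date columns; only the derived times beside them need to match.

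The cost is a few lines of SAP text and a programming check. The listings already plan for symptom and PCR dates, so no new data collection is needed.
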